### **Charge of the Board DSMB**

The purpose of the DSMB will be to provide oversight on the human subject issues described in the protocol, including review (overall and by condition) of the number and type of adverse and serious adverse events. The trial is focusing exclusively on two high risk groups, Hispanic females and Hispanic LGBT youth with a history of self-harm. Adverse events that will be monitored include, but are not limited to psychiatric hospitalizations, suicidal attempts, arrests and child abuse, including sexual abuse. The DSMB will be blinded to condition but will review the number of adverse and serious adverse events by condition in group format. If it becomes apparent that there may be an imbalance by condition, the DSMB will offer its recommendation to the PI regarding the conduct of the trial. Any action that results in the temporary or permanent suspension of the trial will be undertaken with consultation with the study's NIMHD project officer and University of Miami's IRB. The DSMB will provide a copy of the meeting's minutes to the PI.

The University of Miami IRB will provide general study oversight for all grant activities. The Principal Investigator will report DSMB activity to NIMHD as part of the Annual Progress Report.

### **Statement of No Conflicts of Interest**

None of the DSMB members have any conflicts of interest to report, other than they are faculty at the University of Miami.

#### **Frequency of Meetings**

Drs. [name], [name], and [name] will convene as a DSMB three times a year (i.e., every four months).

### PI Acknowledgment of Requirement to Report DSMB Activity

[name], the Principal Investigator, understands that he is required to report DSMB activity in the Annual Progress Report to NIMHD.

The DSM and DSMB reports will include the participants' sociodemographic characteristics, treatment retention rates, any quality assurance or regulatory issues that occurred during the previous year, a summary of AEs and SAEs (Adverse Events and Serious Adverse Events), and any actions or changes with respect to the protocol. The DSM report to NIMHD will also include, when available, the results of any efficacy data analyses conducted. The PI will also: 1) determine if an AE or SAE was study related and to what degree, 2) determine whether an AE or SAE that are study related are listed in the Informed Consent Form or should be listed, 3) ensure that when the AE or SAE was discovered, if it was related and/or possibly related to the study procedures that there was timely and complete reporting to IRB.

AEs and SAEs are sometimes more difficult to identify in behavioral research with adolescents. Based on our experience working with high-risk youth, we have identified common AEs and SAEs that occur in this population, that will be used in training staff to identify AEs and SAEs, and that will be reported during protocol implementation.

- Adverse Events 1. Arrest 2. Runaway 3. Kicked out of Home 4. School Suspension/Expulsion related) 5. Violence (Victim/Exposure)

- Serious Adverse Events
- 6. Physical/Sexual Abuse
- 7. Suicidal Behavior
- 8. Homicidal Behavior
- 9. Hospitalization (psychiatric, drug
- 10. Death
- 11. Other (indicate if serious)

Adverse events for this study may be identified during regularly scheduled intervals or may be reported at any other times during the study. For adolescents and their parent/caregivers that are participating in assessments, the ten adverse events listed above will be queried specifically at T2 and T3 time points. An "other" category has been included to capture unexpected adverse events reported by participants, which do not fall

within the scope of any of the ten defined AEs/SAEs for this study. All assessments conducted by the study assessor are opportunities for identifying adverse events if reported by the participant and/or a family member. The assessor will be trained to identify AEs and SAEs at each of the time points. Additionally, anytime during the study, a participant or his/her family member may report an AE/SAE to their therapist. These events will be identified, classified as serious or not, and will be handled in the same manner as AEs/SAEs during the formal assessments.

Therapists will be trained to identify adverse events, and categorize serious adverse events, based on direct reporting during sessions. Upon identification of an adverse event, the assessor or therapist should categorize the event for seriousness to guarantee that appropriate care and reporting occur within approximately 24 hours. As soon as an adverse event is identified either by querying or direct report, the event will be recorded in the AE log. In addition, the PI and Clinical Supervisor at the site will be notified of any and all AEs. In both treatment conditions, action may be taken by the therapist to respond to non-serious events (e.g., booster sessions, or increase in the frequency of sessions). If a therapist is the one to identify the event, after notifying the PI and Clinical Supervisor, they are to notify and inform the assessor, who is then responsible for conducting further evaluations and completion of the AE log. All non-serious adverse events require no further reporting. Adverse events will be reviewed by the Principal Investigator (PI) weekly to evaluate relatedness to the intervention and whether resolution occurred. Ser"serious and non-serious events that are

SAE's include 1) Physical/Sexual Abuse 2), Suicidal Behavior, 3) Homicidal Behavior, 4) Hospitalization (psychiatric or drug related), and 5) Death. All of these problems may involve imminent danger to self or other. In cases of current suicidal, homicidal, and abusive behaviors, participants in both conditions will be immediately referred to the clinical supervisor to ensure that appropriate crisis intervention services are provided. Serious adverse events listed in this study will also be reported for any family participant. The reporting procedures for SAEs experienced by any participant in the study will be in accordance with the University of Miami IRB reporting policy and determining whether they are unexpected and probably related or expected and non-related will guide reporting. When an SAE occurs, the Clinical Supervisor and the PI must be notified when possible within 2 hours of identification. The Clinical Supervisor will be responsible for ensuring appropriate and timely care of participants. The PI will be responsible for assessing relatedness to the intervention and forwarding the report to the UM IRB and study sponsor. In the event that a participant either withdraws from the study or the PI decides to discontinue a participant due to an SAE, the participant will be monitored by the PI via ongoing status assessment until 1) a resolution is reached or 2) the SAE is determined to be clearly unrelated to the study intervention. Outcomes of the SAE will be reported to the sponsor on a quarterly basis. A summary of the SAEs that occurred during the previous year will be included in the annual progress report to the sponsor.

Study assessors will contact participants in the TAU condition one time per month via telephone to monitor AEs and SAEs that may have occurred as well as to offer referrals

to the youth/family if needed. The procedures to be followed by the assessor are detailed below.

Telephone contact:

The assessor will contact the parent figure and the adolescent and will speak to each one separately.

Questions to Ask Parent

- How has \_\_\_\_\_ been doing in the last month?
- Has there been a change in the problems that brought \_\_\_\_\_ to our program?
- Questions should be specific to intake assessment e.g. ADHD, Depression, Anxiety, Violent or Aggressive Behavior, Drug use, Suicidal thinking, gestures or attempts, etc.
- If there has been a deterioration in functioning in core area (school, peers, severe family conflict) ask for specific behaviors or incidents that occurred in the last 4 weeks. (Check for occurrence of AEs and SAEs)
- Has the youth been attending therapy?
- Has the youth been admitted to a crisis or inpatient treatment program?

Questions to ask Adolescent

- How have you been doing in the last month?
- You were having some problems with (ADHD, Depression, Anxiety, Violent or Aggressive Behavior, Drug Use, Suicidal thinking, gestures or attempts, Self harm without suicidal intent, etc.) when you first came in, how are you doing today?
- Have things become worse or better for you?
- If there has been a deterioration in functioning in a core area (school, peers, severe family conflict) ask for specific behaviors or incidents that occurred in the last month. (Check for occurrence of AEs and SAEs)
- Have you been attending therapy?
- Have you been admitted to a crisis or inpatient treatment program?

Criteria for Referral (\*\*if not currently attending therapy\*\*)

- Suicidal thinking, gestures or attempts
- Self-Harm without Suicidal Intent
- Violent or Aggressive Behavior
- Moderate to Severe Depression
- Moderate to Severe Anxiety
- Significant Deterioration in School Functioning (may be related to ADHD or other problems)
- Significant Increase in Drug Use
- Significant Deterioration in Family Functioning

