## 8) Study Timelines\*

Both conditions will be tested as 16-week interventions. There will be an additional 8-week period of continuing care, then 6 months of no contact, followed by a final assessment. The final assessment will occur 12 months after baseline. The duration of an individual subject's participation in the study will be 1 year (including all follow-up assessments).

The duration anticipated to enroll all study subjects is 35 months. Recruitment will begin in month 8 of the study and end in month 43.

The estimated date for the investigators to complete this study (including primary analyses) is 60 months.

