
#### Therapist Supervision and Adherence Monitoring. Weekly clinical

supervision/consultation meetings will be held for the CA-CIFFTA, led by [name]. Recorded therapy sessions will be reviewed and good manual implementation will be emphasized. In the CA-CIFFTA condition, reports generated weekly showing usage (in minutes) of the web-based components will be reviewed. An independent adherence rater trained to rate therapy sessions will randomly select 20% of the CA CIFFTA sessions at different phases (early, mid, and late) of treatment. Ratings that fall below adequacy on any dimension/component will trigger increased supervision focus for that dimension and if necessary, re-training. The condition supervisor will be the gold-standard for inter-rater reliability on adherence ratings and raters will be trained to achieve an intra-class correlation coefficient of .70 or higher, and at least 80% agreement across items. Interrater reliability will be checked regularly to avoid drift.

Prevention of Dropouts from the study. To ensure sample retention procedures include: 1) conducting assessments at convenient locations when necessary(e.g., homes), 2) paying families for their participation in assessments, 3) conducting service utilization phone interviews between the T2 and T3 assessments and updating all contact information at regular intervals, 5) obtaining the names of three contact persons who may be contacted by the Assessment Specialist when the family is unreachable (included in the consent form), and 6) sending out birthday and holiday cards to all participants. In our experience, the utilization of such procedures for tracking and contacting participants dramatically increase retention rates in the study. In our previous large NIDA randomized trial with high–risk Hispanic youth with Substance Abuse Disorder, we were successful at obtaining approximately 75% of the caregiver and 70% of the adolescent scheduled assessments 16 months after baseline.

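### The ten-event safety query depends on attending T2 and T3, and scheduled adverse-event calls are stated for TAU only, so ascertainment differs by attendance and by arm

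*Protocol*

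**What the plan says.** The protocol lists ten adverse and serious adverse events, plus an open category, under PI Acknowledgment of Requirement to Report DSMB Activity. They include running away, being put out of the home, abuse, suicidal behaviour, hospitalisation and death. The active query is described this way: "For adolescents and their parent/caregivers that are participating in assessments, the ten adverse events listed above will be queried specifically at T2 and T3".

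Other routes appear in the protocol:

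- **Any-time reporting.** "Adverse events for this study may be identified during regularly scheduled intervals or may be reported at any other times during the study". Also: "Additionally, anytime during the study, a participant or his/her family member may report an AE/SAE to their therapist".
- **Monthly calls in TAU.** Assessors telephone TAU families once a month "via telephone to monitor AEs and SAEs that may have occurred as well as to offer referrals". "The assessor will contact the parent figure and the adolescent and will speak to each one separately". Both scripts ask about crisis or inpatient admission. The check for AEs and SAEs is prompted by reported deterioration; the ten events are not read out.
- **Service-use phone interviews between T2 and T3.** These are listed under Prevention of Dropouts from the study (section 10) as a retention measure. They are not limited to one arm, and no adverse-event question is attached to them.
- **Monitoring by the PI** of a participant who leaves because of an SAE.

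Section 8 describes 16 weeks of treatment, 8 weeks of continuing care, "then 6 months of no contact, followed by a final assessment". The DSMB "will review the number of adverse and serious adverse events by condition in group format" and advises the PI if an imbalance appears. The listed contents of the safety reports include treatment retention rates and an AE/SAE summary, but not how many youths were asked about events. The SAP contains no adverse-event analysis.

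**The concern.** A count of events by condition can be compared between arms only if both arms were asked in the same way and the reader knows how many were asked. Here the one query that covers all ten events is stated for families who attend, and the one other scheduled adverse-event contact is stated for one arm.

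Several listed events could plausibly make a family miss a visit. The documents neither state nor quantify this, but if it is so, the query is missing more often where there is something to find. A bare count cannot separate a youth with no event from a youth whose family was not asked. In a trial whose primary endpoint is self-harm, a difference between arms in recorded events could then reflect contact rather than harm, and a real difference could be hidden.

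**Working it through.** The documents give no figure for this point, so there is none to reproduce. The check is a comparison of the routes, followed by an illustration of size.

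**Step 1. Routes open to a family that has stopped attending**

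| Route | TAU | CA CIFFTA |
|---|---|---|
| Ten-event query at T2 and T3 | Stated for those assessed | Stated for those assessed |
| Scheduled monthly AE/SAE call | Yes, not stated to depend on T2/T3 attendance | None stated |
| Spontaneous report to therapist | Passive | Passive |
| Service-use phone interview, T2 to T3 | No AE question stated | No AE question stated |
| PI monitoring after an SAE-related exit | Only for an SAE already known | Only for an SAE already known |

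Scheduled CA CIFFTA contact runs for 16 + 8 = 24 weeks. In the six months that follow, a non-attending CA CIFFTA family has no active adverse-event query in the visible text. A TAU family may still receive monthly calls. The protocol does not explain how those calls fit with the no-contact period in section 8.

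**Step 2. How many families might go unasked**

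Inputs: 100 youths (section 6) and, from the team's earlier trial, "we were successful at obtaining approximately 75% of the caregiver and 70% of the adolescent scheduled assessments 16 months after baseline". Assumption: these rates apply at T3 (12 months), with one caregiver counted per family. Non-completion is a = 1 − 0.70 = 0.30 for adolescents and c = 1 − 0.75 = 0.25 for caregivers.

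Both reporters are queried, so a family is unasked only if both are missing:

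- Lower bound: max(0, a + c − 1) = max(0, −0.45) = 0 per 100.
- Upper bound: min(a, c) = 0.25, or 25 per 100.
- If the losses are independent: a × c = 0.30 × 0.25 = 0.075, or 7.5 per 100.

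Parent and adolescent are assessed at the same visit and swap places (section 10), so missed visits will tend to be joint. That makes independence unlikely and points above 7.5.

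**Step 3. Share of events in those families**

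Let m be the unasked share and RR the event risk in unasked families relative to the rest. RR is assumed; the documents give no value. Share = m × RR / (m × RR + 1 − m).

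| RR | m = 0.25 | m = 0.075 |
|---|---|---|
| 1 | 0.25 / 1.00 = 25% | 0.075 / 1.000 = 7.5% |
| 2 | 0.50 / 1.25 = 40% | 0.150 / 1.075 = 14% |
| 3 | 0.75 / 1.50 = 50% | 0.225 / 1.150 = 20% |

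These are shares of events in the period covered by the missed query, not of all events in the trial. Events before T2 are open to the T2 query in families who attended it. The figures show where events would lie, not how many would be lost, because other routes would recover some.

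**The case against.** The best reply is that the query sentence does not exclude anyone. Its reference to people taking part in assessments may only identify which household members are asked, and the protocol says events can be reported at any time. Therapists are trained to recognise events, TAU families are called monthly, service-use interviews could bring an admission to light, and three contact persons are held for tracing. Part of the safety section is not in the text available for review, and one sentence on event handling breaks off, so further rules cannot be ruled out. The completion figures come from a different trial at a later time point. Families whom tracing has failed to reach may not answer another call.

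Much of this stands, and it rules out three stronger readings that a reader might infer:

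- **That youths who ran away, were hospitalised or died are the ones least likely to be queried.** The caregiver is asked directly and can report such events while in contact. Caregiver report is weaker for abuse or being put out of the home, where the caregiver may be an involved party. No passage ranks youths by likelihood of being asked.
- **That 25 to 30 youths per 100 would go unasked.** With 75 of 100 caregivers responding, no more than 25 families can lack both reporters.
- **That an unasked youth is counted as event-free.** No passage says so, and no denominator is specified.

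The reply does not supply an active query for a non-attending CA CIFFTA family, or a reason why scheduled safety calls are stated for one arm.

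**Conclusion.** The point holds in limited form. In the visible text, the ten-event query is stated only for those taking part in T2 and T3, and scheduled adverse-event calls only for TAU. Active ascertainment therefore depends on attendance and differs by arm, most clearly for CA CIFFTA families in the six months after continuing care. The DSMB is asked to detect imbalance from counts by condition, without a stated number queried.

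The size is uncertain: 0 to 25 families per 100 with neither reporter asked at T3. They would hold 25% to 50% of that period's events at the upper bound and 7.5% to 20% at 7.5 families. This rests on borrowed completion rates and assumed risk ratios of 1 to 3. The direction of any bias between arms cannot be determined from the documents. The point is worth correcting because the remedy is cheap, not because a large loss has been shown.

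**What to change.** 1. State that the ten events are queried for every randomised youth in both arms at the T2 and T3 due dates, whether or not the assessment is completed. Where it is missed and contact has not been refused, ask the parent figure and, where reachable, the adolescent by telephone.
2. Add the same ten-event query to the service-use phone interviews between T2 and T3 in both arms, so that the conditions share a common scheduled query. Record the source of each event, so that those found only through the TAU monthly call can be shown separately.
3. In each DSMB table, show per condition the number of youths queried and the number with unknown status beside the event count.
4. Reconcile the TAU monthly calls and the service-use interviews with the no-contact period in section 8.

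The SAP is dated 8/21/24 and written in the past tense. If follow-up has ended, the collection changes come too late, but the queried and unknown numbers can still be reported with the event counts.

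The cost is some short calls by existing assessors, a few added questions in interviews already planned, and extra table columns. Recovery will be limited in families who cannot be reached; the unknown column at least makes that visible.

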## 9) Study Endpoints\*

- 1. Primary
  - a. Self-harm
- 2. Secondary:
  - a. Depression
  - b. Family functioning
  - c. Alcohol/substance use
  - d. Emotional dysregulation
  - e. Risky sexual behaviors

There are no safety endpoints in this study.

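### Between assessments, adverse events reach the log by different routes in the two arms, so the DSMB's by-condition counts also reflect how events were found

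*Protocol*

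**What the plan says.** The adverse event text sits in the Protocol under the heading PI Acknowledgment of Requirement to Report DSMB Activity. It describes three routes by which an event can reach the log.

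- **Common query.** For adolescents and caregivers who take part in assessments, "the ten adverse events listed above will be queried specifically at T2 and T3 time points". This does not depend on arm.
- **Therapist report.** At any time "a participant or his/her family member may report an AE/SAE to their therapist". The text adds: "Therapists will be trained to identify adverse events, and categorize serious adverse events, based on direct reporting during sessions". Section 10 offers CIFFTA families weekly therapist time over 16 weeks. TAU families are treated by community agencies.
- **Monthly assessor call.** Assessors phone families in the "TAU condition one time per month", both to check for events and to offer referrals. Parent and youth are spoken to separately from a script. No end date is given, and no matching call is described for CIFFTA.

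Events from querying and from direct report go into the same log, and no field for the source is mentioned. Under Charge of the Board DSMB, members are blinded to condition but see the number of events by condition: "If it becomes apparent that there may be an imbalance by condition, the DSMB will offer its recommendation to the PI". Section 9 states: "There are no safety endpoints in this study". The SAP contains no adverse event analysis.

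**The concern.** A comparison of event counts between arms is interpretable only if an event in one arm is about as likely to be recorded as the same event in the other. Here, apart from T2 and T3, the arms are watched differently. TAU has infrequent but scripted assessor calls. CIFFTA has frequent contact in which events surface if someone reports them.

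The DSMB then acts on the counts. Because it is blinded to condition, it cannot discount one group's total for closer surveillance. The events include suicidal behaviour and psychiatric hospitalisation, so either error matters: an imbalance produced by detection could prompt a recommendation, or a real imbalance could be masked.

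**Working it through.** The documents give no expected event rate, no imbalance threshold and no detection rate, so there is no stated figure to reproduce. The check has three parts.

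**1. Scheduled contacts between assessments.** One month is 365.25 / 12 / 7 = 4.35 weeks.

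- Treatment phase, 16 weeks: about 16 CIFFTA therapist sessions (section 10) against 16 / 4.35 = 3.7 TAU assessor calls.
- To the end of continuing care, 24 weeks: 24 / 4.35 = 5.5 TAU calls.
- After week 24: no scheduled CIFFTA therapist contact. TAU calls may or may not continue. Section 8 describes six months without contact, which does not fit calls that have no stated end.

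These are not like-for-like counts. The session route relies on spontaneous report. The TAU call asks directly about inpatient or crisis admission, but ties its wider event check to reported deterioration. Neither is the ten-event query. TAU families also receive therapist phone calls during continuing care. The service-utilization interviews between T2 and T3 are not arm-specific and could reveal hospitalisations in either arm.

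**2. How far the common query limits the distortion.** All rates here are assumptions: equal true risk of 30% in both arms, 50 youth per arm (100 in total; the allocation ratio is not stated), and each youth counted once. Completion of T2/T3 is set at 70%, the adolescent figure from the team's earlier trial at 16 months (section 10, dropout prevention). With between-visit detection b and recall r at T2/T3,

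detection = 1 − (1 − b)(1 − 0.70 r), and expected count = 50 × 0.30 × detection.

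With b = 0.9 in one arm and 0.5 in the other:

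| Recall r | Detection | Expected counts | Ratio | Chance of a gap of 5 or more in that direction |
|---|---|---|---|---|
| 0 (query finds nothing) | 0.900 v 0.500 | 13.50 v 7.50 | 1.80 | 0.65 |
| 0.5 | 0.935 v 0.675 | 14.03 v 10.13 | 1.39 | 0.44 |
| 0.8 | 0.956 v 0.780 | 14.34 v 11.70 | 1.23 | 0.34 |
| 1.0 | 0.970 v 0.850 | 14.55 v 12.75 | 1.14 | 0.27 |
| 1.0, with 100% completion | 1.000 v 1.000 | 15.00 v 15.00 | 1.00 | 0.16 |

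The last column is exact binomial. The bottom row is what chance alone produces with full, equal detection. A milder gap (0.7 v 0.5) gives ratios of 1.19, 1.11 and 1.07 at recall 0.5, 0.8 and 1.0 with 70% completion. Swapping the arms turns 1.39, 1.23 and 1.14 into 0.72, 0.82 and 0.88.

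**3. When the common query is available.** It falls at 4 and 12 months after baseline. The DSMB meets every four months, and enrolment runs for 35 months. At a typical meeting, many youth will be between queries, and their events will have arrived only through the unequal routes.

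**The case against.** The strongest defence has five parts.

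- **The common query exists.** All ten defined events are asked about in both arms at T2 and T3. This stands, and it is why the distortion in the illustration shrinks from 1.80 to between 1.14 and 1.39. It does not vanish unless completion and recall are full.
- **The therapist route is not written as CIFFTA-only.** The protocol says "In both treatment conditions, action may be taken by the therapist" and describes coordination with TAU agencies. This stands too. A reader might infer that TAU therapists are untrained in event reporting. The documents show only that no such training of community staff is described.
- **The absence of CIFFTA calls is read from silence.** Part of the safety section was not in the text available for this review, and one sentence there breaks off. The claim is therefore limited to what is described.
- **The calls are a sensible safeguard for youth treated off site.** They are, and nothing here argues against them. The issue is how their yield is tabulated.
- **No rule forces action.** The DSMB only recommends, and a suspension requires consultation with the funder and the IRB. This lowers the stakes, but the comparison still informs the recommendation.

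A further objection limits the remedy. The T2/T3 query reaches only those assessed. Youth who died, withdrew, or were removed for self-harm risk (section 14) may never be asked. A comparison resting on that query alone would exchange unequal detection for informative missingness in the gravest events.

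**Conclusion.** The narrow point holds. As described, between-visit ascertainment differs by arm, and the DSMB judges imbalance from counts that do not distinguish source. Those counts therefore also reflect how events were found.

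A reader might go further and infer that the safety comparison says as much about who was asked as about what happened, or that CIFFTA is set up to show a false harm signal. The documents support neither. The illustrated ratios run from 1.00 to 1.80, or down to 0.56 if the arms are swapped, and all depend on assumed detection, recall, completion and event rates. CIFFTA contact is more frequent but passive; TAU contact is rarer but scripted. The direction is unknown and may change after week 24.

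This is a reporting weakness that is cheap to repair. It is not a flaw that invalidates the trial's safety oversight.

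**What to change.** Leave all monitoring and individual event reporting as they are, and change only the recording and tabulation.

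- **Log:** record the source of each event (T2/T3 query, monthly call, therapist, other). The SAP is dated 8/21/24 and written in the past tense, so for events already logged the source would have to be recovered from contact notes where these exist.
- **DSMB charge, SAP and final report:** show counts by condition split by source. Present events from the T2/T3 query as the like-for-like comparison: the proportion of those queried, with a 95% CI and the numbers queried and randomised per arm. Place it beside the all-source totals, not in their stead, and always show deaths and events in youth who were not assessed.
- **Consistency:** reconcile the monthly TAU calls, which have no stated end, with the six-month period without contact in section 8.

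The cost is one log field and a longer table. The like-for-like comparison uses fewer events, exists only at T2 and T3, and is exposed to missing assessments. Since the calls are described for TAU only, a full split by source would reveal the arms to a blinded board. A two-row version (T2/T3 query, any other source) avoids naming the call, with the full split kept for the final report or for a board that agrees to see it.

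### The only explicit AE/SAE check in the monthly TAU call depends on reported deterioration, so abuse, victimisation and arrest need not be specifically asked about until T2 or T3

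*Protocol*

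**What the plan says.** The safety-monitoring text of the Protocol (under PI Acknowledgment of Requirement to Report DSMB Activity) lists ten named AEs and SAEs plus an open category for others. For adolescents and caregivers who take part in assessments, "the ten adverse events listed above will be queried specifically at T2 and T3". Events may also be reported at any other time, including to a therapist.

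The same text adds a contact for one arm only. Assessors telephone families in the "TAU condition one time per month", and the stated purpose is "via telephone to monitor AEs and SAEs that may have occurred as well as to offer referrals". It says that the procedure the assessor must follow is the script set out beneath it.

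The parent script has a line beginning "If there has been a deterioration in functioning in core area (school, peers, severe family conflict) ask for specific behaviors or incidents", which continues "that occurred in the last 4 weeks. (Check for occurrence of AEs and SAEs" and there closes its parenthesis. The adolescent script has the matching line "If there has been a deterioration in functioning in a core area (school, peers, severe family conflict) ask for specific behaviors or incidents", with the same event check at its end. Neither script contains another explicit AE/SAE prompt.

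Both scripts also contain questions without that condition: how the youth has been over the past month, how the problems present at intake now stand, whether the youth attends therapy, and whether there has been a crisis or inpatient admission.

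**The concern.** The purpose of the call and its script do not match. The call exists to find events, but the instruction to look for them applies only when someone has already reported a decline. A listed event that the family does not see or describe as a decline in school, peers or family life gets no specific question, and the call can end with nothing recorded.

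Two things are at stake. One is timeliness: the Protocol's response times (about 24 hours for care and reporting, and notification of an SAE within 2 hours where possible) run from identification, so an event that is not asked about starts no clock. The other is the comparison of arms: the DSMB reviews numbers of events by condition (Charge of the Board DSMB) three times a year (Frequency of Meetings), and those numbers depend on how events are looked for in each arm.

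**Working it through.** There is no planned figure to reproduce. The check sets the ten named events against the questions that the script asks of everyone.

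| Listed event | Covered by an unconditional question in the call? |
|---|---|
| Hospitalization | Yes, directly: the admission question goes to parent and adolescent |
| Suicidal behavior | Indirectly: status of intake problems |
| Homicidal behavior | Possibly, indirectly: violent or aggressive behavior is among the intake-problem examples |
| Arrest | Not named |
| Runaway | Not named |
| Kicked out of home | Not named |
| School suspension/expulsion | Not named |
| Violence (victim/exposure) | Not named |
| Physical/sexual abuse | Not named |
| Death | No question, but a youth's death would be expected to emerge on contact |

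Tally: 1 direct + 2 indirect + 6 not named + 1 (death) = 10.

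**How far the condition reaches.** Three of the six unnamed events (suspension or expulsion, running away, being put out of the home) could well be reported as trouble at school or in the family, and so trigger the conditional line. That leaves 6 − 3 = 3 for which the trigger is least dependable: abuse, violence victimisation and arrest. Abuse is a listed SAE.

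**When the next specific query comes.** Section 10 (Measures) places T2 at 4 months and T3 at 12 months after baseline. An event soon after baseline can wait up to 4 months for the ten-event query; one soon after T2 can wait up to 12 − 4 = 8 months.

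**Whom that query reaches.** It is limited to families who are assessed. Section 10 (Prevention of Dropouts) reports that an earlier trial by the same team obtained about 70% of scheduled adolescent assessments at 16 months. That was a different study with a longer horizon, so it only indicates that some T3 assessments will be missed. A TAU family that misses T3 but answers the telephone would never get the ten-event query after T2.

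**Whether the calls run throughout.** Section 8 describes 16 weeks of treatment and 8 weeks of continuing care (16 + 8 = 24 weeks), then six months without contact before the final assessment. The safety text gives no end date for the monthly calls. The two cannot both apply as written over that last half-year.

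**The case against.** The strongest case on the other side has five parts.

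- *A reader might infer that no event is asked about unless deterioration is reported.* The documents do not support that. Admission is asked of everyone. Every participant enters with self-reported self-harm in the past 6 months (Section 5), and Section 4 counts nonfatal suicide attempts as self-harm, so the intake-problem question has a self-harm referent for every youth. The adolescent is also asked whether things have improved or worsened. For a youth not in therapy, the referral criteria require the assessor to establish suicidal, self-harming and violent behaviour. What stands is narrower: these questions ask about current status, not whether an event happened.
- *The parenthesis may be a general reminder to the assessor.* That is possible, but its identical placement in both scripts favours the conditional reading. At best the text is ambiguous on the main purpose of the call.
- *There are other routes.* T2 and T3 query all ten events, TAU families receive further telephone calls during continuing care (Section 10), and a therapist may report an event at any time. A reader should therefore not infer that the monthly call is the only safety contact after T2. But the continuing-care calls are not described as event checks, and the Protocol does not say that community therapists in TAU receive the study's AE training.
- *A reader might infer uncovered days from a four-week look-back at monthly calls.* The opening questions and the adolescent line refer to the past month, and the admission question has no time limit. The difference is loose wording and no measured gap follows from it.
- *An event may be volunteered at this or a later call.* True. The documents give no figure for how often, so the share of events missed cannot be estimated.

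**Conclusion.** The point holds in limited form. The stated purpose of the TAU call and its script disagree: the only explicit AE/SAE check is conditional on reported deterioration. Apart from crisis or inpatient admission and the open status of intake problems, the listed events are not specifically asked about until T2 or T3. Six of ten are named in no unconditional question, and three of these (abuse, victimisation, arrest) are the clearest gap. The delay to a specific query can reach 8 months, and for families who miss T3 there is no such query after T2.

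This rests on reading the parenthesis as part of the sentence that contains it, and on assessors following the script as written. The number of events affected is unknown, and the documents do not show that any event would be lost to the trial altogether. The direction of any effect on the by-arm comparison cannot be determined from the text either. It is a correction worth making to a safety script, and does not show that safety monitoring as a whole fails.

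**What to change.** In both scripts, take the event check out of the deterioration line and make it a separate item at every call: go through the ten listed events and the open category for the time since the last completed call or assessment. That one reference period also removes the mixed four-week and one-month wording.

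Record the source of each event (monthly call, therapist, or T2/T3 query). Keep reporting all events to the DSMB. Use the source only to show a like-for-like comparison by arm alongside the full counts. Counts by arm should not rest on the T2/T3 query alone: that would leave out events found by calls or therapists and count nothing for youths who miss assessments.

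The sponsor should also reconcile the monthly calls with the no-contact period in Section 8 and state when the calls end. If the calls are already complete, as the SAP's date (8/21/24) and past tense suggest, the source of each event should still be recorded where it is known, and this limit on ascertainment stated when TAU events are reported.

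The cost is a change of script wording, a few more minutes per call with existing staff, and more TAU events to log. Fuller calls may raise the TAU count by themselves, which the recorded source makes visible.
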